5.4.3 Reporting Requirements for Pregnancies

5.4.3.1 Pregnancies in Female Patients

Female patients of childbearing potential will be instructed to immediately inform the investigator if they become pregnant during the study or within 5 months after the final dose of study treatment. A paper Clinical Trial Pregnancy Reporting Form should be completed and submitted to the Sponsor or its designee immediately (i.e., no more than 24 hours after learning of the pregnancy), either by faxing or by scanning and emailing

the form using the fax number or email address provided to investigators. Pregnancy should not be recorded on the Adverse Event eCRF. The investigator should discontinue study treatment and counsel the patient, discussing the risks of the pregnancy and the possible effects on the fetus. Monitoring of the patient should continue until conclusion of the pregnancy. Any serious adverse events associated with the pregnancy (e.g., an event in the fetus, an event in the mother during or after the pregnancy, or a congenital anomaly/birth defect in the child) should be reported on the Adverse Event eCRF. In addition, the investigator will submit a Clinical Trial Pregnancy Reporting Form when updated information on the course and outcome of the pregnancy becomes available.

5.4.3.2 Pregnancies in Female Partners of Male Patients

Male patients will be instructed through the Informed Consent Form to immediately inform the investigator if their partner becomes pregnant during the study or within 120 days after the final dose of study treatment. A paper Clinical Trial Pregnancy Reporting Form should be completed and submitted to the Sponsor or its designee immediately (i.e., no more than 24 hours after learning of the pregnancy), either by faxing or by scanning and emailing the form using the fax number or email address provided to investigators. Attempts should be made to collect and report details of the course and outcome of any pregnancy in the partner of a male patient exposed to study treatment. When permitted by the site's IRB, the pregnant partner would need to sign an Authorization for Use and Disclosure of Pregnancy Health Information to allow for follow-up on her pregnancy. If the authorization has been signed, the investigator should submit a Clinical Trial Pregnancy Reporting Form when updated information on the course and outcome of the pregnancy becomes available. An investigator who is contacted by the male patient or his pregnant partner may provide information on the risks of the pregnancy and the possible effects on the fetus, to support an informed decision in cooperation with the treating physician and/or obstetrician.

5.4.3.3 Abortions

A spontaneous abortion should be classified as a serious adverse event (as the Sponsor considers abortions to be medically significant), recorded on the Adverse Event eCRF, and reported to the Sponsor immediately (i.e., no more than 24 hours after learning of the event; see Section [5.4.2](#)).

If a therapeutic or elective abortion was performed because of an underlying maternal or embryofetal toxicity, the toxicity should be classified as a serious adverse event, recorded on the Adverse Event eCRF, and reported to the Sponsor immediately (i.e., no more than 24 hours after learning of the event; see Section [5.4.2](#)). A therapeutic or elective abortion performed for reasons other than an underlying maternal or embryofetal toxicity is not considered an adverse event.

All abortions should be reported as pregnancy outcomes on the paper Clinical Trial Pregnancy Reporting Form.

5.4.3.4 Congenital Anomalies/Birth Defects

Any congenital anomaly/birth defect in a child born to a female patient exposed to study treatment or the female partner of a male patient exposed to study treatment should be classified as a serious adverse event, recorded on the Adverse Event eCRF, and reported to the Sponsor immediately (i.e., no more than 24 hours after learning of the event; see Section 5.4.2).

5.5 FOLLOW-UP OF PATIENTS AFTER ADVERSE EVENTS

5.5.1 Investigator Follow-Up

The investigator should follow each adverse event until the event has resolved to baseline grade or better, the event is assessed as stable by the investigator, the patient is lost to follow-up, or the patient withdraws consent. Every effort should be made to follow all serious adverse events considered to be related to study treatment or trial-related procedures until a final outcome can be reported.

During the study period, resolution of adverse events (with dates) should be documented on the Adverse Event eCRF and in the patient's medical record to facilitate source data verification.

All pregnancies reported during the study should be followed until pregnancy outcome.

5.5.2 Sponsor Follow-Up

For serious adverse events, adverse events of special interest, and pregnancies, the Sponsor or a designee may follow up by telephone, fax, email, and/or a monitoring visit to obtain additional case details and outcome information (e.g., from hospital discharge summaries, consultant reports, autopsy reports) in order to perform an independent medical assessment of the reported case.

5.6 ADVERSE EVENTS THAT OCCUR AFTER THE ADVERSE EVENT REPORTING PERIOD

After the end of the reporting period for serious adverse events and adverse events of special interest defined as 135 days after the final dose of study treatment or until initiation of new systemic anti-cancer therapy, whichever occurs first), all deaths, regardless of cause, should be reported through use of the Long-Term Survival Follow-Up eCRF.

In addition, if the investigator becomes aware of a serious adverse event that is believed to be related to prior exposure to study treatment, the event should be reported through use of the Adverse Event eCRF. However, if the EDC system is not available, the investigator should report these events directly to the Sponsor or its designee, either by faxing or by scanning and emailing the paper Clinical Trial Serious Adverse Event/Adverse Event of Special Interest Reporting Form using the fax number or email address provided to investigators.

5.7 EXPEDITED REPORTING TO HEALTH AUTHORITIES, INVESTIGATORS, INSTITUTIONAL REVIEW BOARDS, AND ETHICS COMMITTEES

The Sponsor will promptly evaluate all serious adverse events and adverse events of special interest against cumulative product experience to identify and expeditiously communicate possible new safety findings to investigators, IRBs, and applicable health authorities based on applicable legislation.

To determine reporting requirements for single adverse event cases, the Sponsor will assess the expectedness of these events using the following reference documents:

- Atezolizumab Investigator's Brochure
- Hu5F9-G4 Investigator's Brochure

The Sponsor will compare the severity of each event and the cumulative event frequency reported for the study with the severity and frequency reported in the applicable reference document.

Reporting requirements will also be based on the investigator's assessment of causality and seriousness, with allowance for upgrading by the Sponsor as needed.

6. STATISTICAL CONSIDERATIONS AND ANALYSIS PLAN

The primary analysis will be based on patient data collected through study discontinuation or the end of study. All analyses will be based on the safety-evaluable population, defined as all patients who receive any amount of either study drug.

6.1 DETERMINATION OF SAMPLE SIZE

Design considerations covering all cohorts were not made with regard to explicit power and type I error considerations but to obtain preliminary safety, efficacy, PK, and PD information on atezolizumab in combination with Hu5F9-G4. The planned enrollment for this study is 21 patients, depending on the safety profile observed during the safety evaluation phase. The study will enroll approximately 6 patients in the safety cohort and approximately 15 patients in the expansion cohort. The sample size may increase as a result of dose findings. The probabilities of observing adverse events in at least 1 patient, given the varying actual adverse event rates, are listed in [Table 6](#).

Table 7 Probability of Safety-Signal Detection with a Cohort of 21 Patients

True Underlying Probability of an Adverse Event	Probability of Observing at Least One Adverse Event in 20 Patients (%)
0.01	19.0
0.025	41.2
0.05	65.9
0.075	80.5
0.1	89.1

6.2 SUMMARIES OF CONDUCT OF STUDY

Enrollment, major protocol deviations, and discontinuations from the study will be summarized descriptively by the assigned dose, schedule, and cohort.

6.3 DEMOGRAPHIC AND BASELINE CHARACTERISTICS

Demographics and baseline characteristics such as age, sex, weight, duration of malignancy, and baseline ECOG Performance Status will be summarized using means, standard deviations, medians, and ranges for continuous variables, and proportions for categorical variables. All summaries will be presented for the overall cohort.

Study drug administration data will be listed by dose and schedule and any dose modifications will be flagged. Means and standard deviations will be used to summarize the total dose of atezolizumab and Hu5F9-G4 received.

6.4 SAFETY ANALYSES

The safety analyses will include all patients who receive any amount of either study drug, with patients grouped as a whole.

Safety will be assessed through summaries of adverse events, change from baseline in targeted vital signs, laboratory test results, and physical examination findings.

All collected adverse event data will be listed by assigned dose level and patient number. All adverse events occurring on or after treatment on Day 1 of Cycle 1 will be summarized by mapped term, appropriate thesaurus levels, and NCI CTCAE v5.0 toxicity grade. In addition, all serious adverse events, including deaths, will be listed separately and summarized. DLTs and adverse events leading to treatment discontinuation will also be listed separately.

6.5 PHARMACOKINETIC ANALYSES

The PK analysis population will consist of all subjects with at least one PK value that can be reported. As appropriate, serum concentrations of atezolizumab and Hu5F9-G4 will be tabulated, summarized, and plotted after appropriate grouping. Additional PK and PK/PD analyses (e.g., population modeling, including pooled analyses across studies)

may also be performed as appropriate. If performed, these additional analyses may be reported separately from the clinical study report. At the discretion of the Sponsor, all analyses may be extended to include relevant biotransformation products of the study treatments administered. Depending on the results from interim PK analyses, the frequency of PK sampling may be reduced later in the study.

6.6 EFFICACY ANALYSES

Response assessment data (ORR, DOR, EFS, LFS, OS, PFS, the rate of transfusion independence, and the duration of transfusion independence) will be summarized for all patients as a single cohort. Time-to-event data will be summarized using Kaplan-Meier methods.

Interim looks may be performed during the study. Response data will be compared with the comparable historical data using statistical methodology such as a predictive and/or posterior probability design (Lee and Liu 2008), with the modification that the uncertainty in the historical control data is fully taken into account by utilizing a distribution on the control response rate to enable internal decision-making for future development. The possible data sources to be used as historical controls may be publications, real-world data sources, and other reliable information on efficacy from other studies in similar patient groups that will be available by the time of the interim analysis.

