3.1.2.2 Rules for Dose Modification and Changes in Dose Scheduling following Dose-Limiting Toxicity

Dose modification following the DLT window will occur in accordance with the following rules:

- The safety cohort will enroll up to 6 patients.
- *If DLTs are observed in ≥33% of patients (i.e., 2 or more of 6 patients) in this initial safety cohort, a dose de-escalation cohort of 6 patients will be enrolled. The dosing schedules for this de-escalation cohort will be as follows:*
 - *Atezolizumab will be administered to patients by IV infusion at a fixed dose of 840 mg, starting on Day 22 of Cycle 1. In subsequent cycles, 840 mg of atezolizumab administered by IV infusion will be given Q2W on Days 8 and 22 of each 28-day cycle.*
 - *Hu5F9-G4 will be given as two priming doses of 1 mg/kg IV on Days 1 and 4, followed by loading doses of 10 mg/kg IV on Day 8 and 15 mg/kg on Day 11. Starting on Day 15, maintenance treatment with Hu5F9-G4 will be given by IV infusion at a dose of 15 mg/kg QW.*
 - *If a DLT is observed in ≥33% of patients (i.e., 2 or more of 6 dose de-escalation patients), the dose and schedule will be considered intolerable and the MTD will have been exceeded.*

- The dose level(s) and schedule at which *<33% of patients (i.e., 1 or fewer of 6 dose de-escalation patients) experience a DLT will be declared the optimal dose and schedule and an expansion cohort of 9 patients will be enrolled using the same dosing regimen.*
- *If DLTs are observed in <33% of patients (i.e., 1 or fewer of 6 patients) in the initial safety cohort, an expansion cohort of 15 patients will be enrolled to further test the safety and anti-tumor activity of atezolizumab in combination with Hu5F9-G4, using the same dosing regimen.*

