4.3.2.2 Hu5F9-G4

The initial priming dose will be administered as a continuous IV infusion in 250 mL of normal saline over 180 minutes to reduce the risk of acute hemagglutination. All other infusions for doses > 1 mg/kg will be administered in 500 mL over 120 minutes. If more than 4 weeks have elapsed since the last dose of Hu5F9-G4 and the patient is to resume treatment, patients must undergo intra-patient dose escalation again of Hu5F9-G4 based on their original dosing regimen (e.g., 1 mg/kg of priming dose on Days 1 and 4, 15 mg/kg on Day 8, and 30 mg/kg on Days 11, 15, and 22).

The dose level of Hu5F9-G4 administered to patients by IV infusion in this study varies according to the week of treatment. Initially, two priming doses of 1 mg/kg will be given on Days 1 and 4 of Cycle 1. This will be followed by loading doses of 15 mg/kg on Day 8, followed by 30 mg/kg on Day 11 of Cycle 1. Starting on Day 15, Hu5F9-G4 maintenance will be given at a dose of 30 mg/kg QW.

Premedication is required before administration of the first four doses of Hu5F9-G4 with 650–1000 mg of oral acetaminophen and 25–50 mg of oral or IV diphenhydramine or comparable regimen.

Recommended safety measures for preparation and handling of Hu5F9-G4 include laboratory coats and gloves. In addition, Hu5F9-G4 cannot be mixed with any other drug in the infusion bag or administration. Hu5F9-G4 should not be administered as a bolus injection.

There have been no late-onset hypersensitivity reactions. Thus, recommendations for potential infusion reactions should follow recommendations from [Table 2](#) (see Section 4.3.2.1). Guidelines for medical management of infusion-related reactions (IRRs) are provided in the [Appendix 8](#).

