6.6.1 Primary Efficacy Endpoint

Primary efficacy endpoints include CR rate (CR+CRp+CRi+CRh) and DOR.

The CR rate will be assessed as the percentage of patients who achieve a CR, CRp, CRi, or CRh (as defined by the IWG 2003 and ELN 2010 criteria) after up to six cycles of combination therapy. The CR rate will be estimated, and the 95% confidence interval will be calculated.

DOR will be analyzed for the subset of patients who achieve an objective response as defined in Section 2.3.1. DOR is defined as the time from the initial response to the time of disease progression or death (whichever occurs first). If a patient is alive and has not experienced progressive disease before the end of the study, DOR will be censored at the day of the last cancer assessment. If no cancer assessments are performed after the date of the first occurrence of an objective response, DOR will be censored at the date of the first occurrence of an objective response plus 1 day.

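### If Hu5F9-G4 is de-escalated, baseline, adverse-event and efficacy summaries still pool both dose levels, and Appendix 8's dose-modification text does not fit the 15 mg/kg cohort

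*Combined protocol and SAP*

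**What the plan says.** **Design.** The first 6 patients are assigned 30 mg/kg weekly Hu5F9-G4 maintenance. If 2 or more have a DLT, 6 further patients are enrolled for whom, under Section 3.1.2.2, "maintenance treatment with Hu5F9-G4 will be given by IV infusion at a dose of 15 mg/kg QW". If at most 1 of those 6 has a DLT, that dose and schedule is declared optimal and 9 expansion patients receive it. Total enrollment is capped at 21, and replaced patients count toward the cap (Section 3.1.2.1).

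**Analysis.**
- Section 6, population: "All analyses will be based on the safety-evaluable population, defined as all patients who receive any amount of either study drug".
- Section 6.3, baseline: "All summaries will be presented for the overall cohort".
- Section 6.4, safety: "The safety analyses will include all patients who receive any amount of either study drug, with patients grouped as a whole".
- Section 6.6, response and time-to-event data: "will be summarized for all patients as a single cohort".
- Section 6.6.1, primary efficacy: "The CR rate will be estimated, and the 95% confidence interval will be calculated". No dose split is mentioned.
- Section 6.2, by contrast: enrollment, major deviations and discontinuations are "summarized descriptively by the assigned dose, schedule, and cohort".

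Dose also appears in the drug-administration listing (6.3), the adverse-event listing (6.4) and the optional biomarker listings (6.8). PK data may be grouped as appropriate (6.5), and ADA results are summarized by treatment group (6.7).

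**Dosing text.** Section 4.3.2.2 says: "Starting on Day 15, Hu5F9-G4 maintenance will be given at a dose of 30 mg/kg QW". Appendix 1 footnote w also gives only 30 mg/kg maintenance. Appendix 8 names one reduced Hu5F9-G4 level, 20 mg/kg, takes patients who need to go lower off Hu5F9-G4, and ties the restart of atezolizumab after repriming to the start of weekly 30 mg/kg dosing. None of this is restricted to a cohort.

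**The concern.** The statements in 6.3, 6.4 and 6.6 direct pooling; they are not merely silent about dose. Section 6.2 shows that the plan recognizes assigned dose as a grouping factor, yet does not use it for the main safety and efficacy results.

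If de-escalation happens, the protocol has judged the higher regimen unacceptable and taken the lower one forward. The adverse-event incidences and response rates in the report would then describe a mixture of the two. The optional interim comparison with historical data in 6.6, intended to inform future development, names no dose level either.

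The same omission appears in the dosing text. For a patient assigned 15 mg/kg, a move to 20 mg/kg is not a decrease, the assigned dose already lies below the level at which Appendix 8 ends Hu5F9-G4, and weekly 30 mg/kg dosing never begins. Sites treating that cohort would be working from provisions written for another dose.

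**Working it through.** **Inputs.** Trigger: at least 2 of 6 (Section 3.1.2.2). Cohorts in the de-escalation branch: 6 + 6 + 9 = 21, so 6 patients at 30 mg/kg and 6 + 9 = 15 at 15 mg/kg. Detection probabilities: Table 7. The true DLT rates are assumptions, since the documents give none for the combination; 20% equals the target toxicity rate in Section 3.1.2.4.

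**1. The plan's own figure.** Table 7 follows 1 − (1 − p)^21: 19.0, 41.2, 65.9, 80.5 and 89.1% at p = 0.01, 0.025, 0.05, 0.075 and 0.10. It reproduces.

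**2. How likely is the branch?** The trigger probability is P(X ≥ 2 | 6, p) = 1 − (1 − p)^6 − 6p(1 − p)^5. The lower dose passes with probability P(X ≤ 1 | 6, p).

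| True DLT rate | Trigger | Pass | 6/15 split, same rate at both doses | Both doses fail, same rate |
|---|---|---|---|---|
| 10% | 0.114 | 0.886 | 0.101 | 0.013 |
| 20% | 0.345 | 0.655 | 0.226 | 0.119 |
| 33% | 0.642 | 0.358 | 0.230 | 0.412 |

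If the lower dose has a 10% DLT rate, the 6/15 split has probability 0.345 × 0.886 = 0.305 when the higher dose has 20%, and 0.642 × 0.886 = 0.569 when it has 33%.

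**3. Share of the pooled tables from the rejected regimen.** 6/21 = 28.6%. One or two replaced patients in the first cohort make it 7/21 = 33.3% or 8/21 = 38.1%. If the lower dose also fails, the split is about 6/12 = 50%, although no retained dose is then left to describe.

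**4. Illustrations with assumed rates.**
- An adverse event in 3/6 at 30 mg/kg and 3/15 at 15 mg/kg pools to 6/21 = 28.6%, against 3/15 = 20.0% at the retained dose.
- Response rates of 30% at 30 mg/kg and 10% at 15 mg/kg pool to (6 × 0.30 + 15 × 0.10)/21 = 15.7%. With 10% and 30%, the pooled rate is (6 × 0.10 + 15 × 0.30)/21 = 24.3%. Neither pooled value describes either dose.

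**5. Detection at the retained dose.** 1 − (1 − p)^15 gives 14.0, 31.6, 53.7, 68.9 and 79.4% at the five rates in Table 7.

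**6. Dosing text against the 15 mg/kg cohort.**

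| Provision | Figure | For a patient assigned 15 mg/kg |
|---|---|---|
| Appendix 8, reduced dose | 20 mg/kg | Higher than the assigned dose (20/15 = 1.33) |
| Appendix 8, Hu5F9-G4 ended if a lower dose is needed | below 20 mg/kg | Assigned dose already below this level |
| Appendix 8, atezolizumab restart after repriming | 30 mg/kg weekly | Not part of this cohort's schedule |
| Section 4.3.2.2 and Appendix 1 footnote w, maintenance | 30 mg/kg | Conflicts with Section 3.1.2.2 |

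**The case against.** **Decisions are not pooled.** DLT decisions are made within each cohort of 6, and the Table 1 stopping boundaries use the expansion cohort's own denominator. This is right: pooling affects the descriptive tables, not the choice of dose or the stopping rule. But descriptive tables are the main product of a study with no power or type I error basis (Section 6.1).

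**By-dose counts could be read off the listings.** Adverse events are listed by assigned dose and patient, so with 21 patients no safety information is lost. A listing is still not an incidence summary, and efficacy has not even a firm by-dose listing, because the biomarker listings in 6.8 are optional.

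**Pooling may be harmless.** Atezolizumab is given identically at both levels. Section 3.3.4 reports that doses of 10 mg/kg or more overcome the CD47 antigen sink, and both maintenance doses exceed that. Section 3.3.2 puts single-agent response at no more than 10%, so a 30% response rate has no support in the documents. The illustrations are therefore only illustrations. The argument bears on efficacy; it gives no reason to expect equal toxicity at a regimen rejected for DLTs.

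**The branch may be unlikely and the distortion small.** Single-agent Hu5F9-G4 data show no remaining DLT in 13 patients and no MTD up to 30 mg/kg twice weekly (Sections 1.4 and 3.3.4). The combination is untested, so higher rates cannot be excluded, but the 33% scenario is an assumption. The exact interval for 3/15 also contains the pooled 28.6%. That reflects the small sample; it does not make the mixture the right quantity to report.

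**Section 4.3.2.2 ties re-escalation to the schedule first assigned to the patient.** That wording can accommodate the lower cohort for re-escalation. It leaves Appendix 8's fixed 20 and 30 mg/kg figures unresolved.

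**Conclusion.** The concern holds in both parts and should be fixed.

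(a) If de-escalation occurs, Sections 6.3, 6.4 and 6.6 as written plan no by-dose baseline, adverse-event or efficacy summary. In the 6/15 split, 29% of the patients in each pooled summary come from the rejected regimen, or up to 38% with two replacements in the first cohort. For the CR rate this is an inference: the list in 6.6 does not name it, but 6.6.1 plans one rate in the single safety-evaluable population. The probabilities rest on assumed DLT rates and independent binomial outcomes. Without de-escalation all 21 patients are assigned one regimen and there is no problem.

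(b) Appendix 8 contradicts the 15 mg/kg cohort in Section 3.1.2.2 whatever the DLT rates. That cohort has no workable reduction provision, and it never reaches the stated condition for restarting atezolizumab after repriming.

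**What to change.** **Analysis.** Add to 6.3, 6.4 and 6.6 that, if de-escalation occurs, baseline, adverse-event and efficacy summaries, including the CR rate and any interim response comparison, are presented by assigned Hu5F9-G4 dose level. Make the dose declared optimal (its safety plus expansion patients) the main presentation and the pooled table supportive. Add a note under Table 7 that n is about 15 at the retained dose in that branch. By-dose columns alone would close the gap; the ordering and the note make the retained dose easier to read.

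**Dosing text.** Reconcile Appendix 8, Section 4.3.2.2 and Appendix 1 footnote w with the 15 mg/kg cohort in Section 3.1.2.2. Which doses or rules should apply is for the sponsor to decide; none is proposed here.

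**Cost.** Two or three conditional sentences in Section 6, table columns needed only if the branch is taken, and reconciling wording in an amendment. By-dose denominators will be small (about 15 and 6) and intervals wide: 3/15 has an exact 95% interval of 4% to 48%.
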